9.4 Interim Analyses and Stopping Rules

No interim efficacy or futility analyses are planned because of the minimal risk level of the study and because patient outcomes are very unlikely to be worse in the intervention group in the study.

This study will be stopped prior to its completion only after discussion with and input from NCCIH if: (1) the intervention is associated with severe adverse effects that call into question the safety of the intervention; (2) difficulty in study recruitment or retention will significantly

impact the ability to evaluate the study endpoints; (3) any new information becomes available during the trial that necessitates stopping the trial; or (4) other situations occur that might warrant stopping the trial.

Pertaining to the likelihood of adverse events, prior studies employing MABT to individuals with mental health concerns including two NIH-funded studies for individuals with substance use disorder, many of whom had moderate-severe depression and/or anxiety symptoms, and three additional studies for women with sexual trauma, have not identified significant risks associated with this intervention. However, should adverse events occur that are determined to be related to study participation, the MPIs and independent monitor (IM) will consult with both the UW IRB and the NICCH Program Officer about the likelihood of continued risk to study participants and will make a decision about whether it is necessary to stop the trial.

Should accrual monitoring demonstrate the need, the MPIs will consult with the data analyst and the IM to assess the impact of significant data loss due to problems in recruitment, retention, or data collection. Factors external to the study when interpreting the data, such as scientific developments or the new availability of proven clinical services that could have an impact on the safety of the participants, the performance of the study or the ethics of the study, will be reviewed by the MPIs annually.

9.5 Outcomes

9.5.1 Primary Outcome

The primary outcome is patient-reported days of abstinence from illicit opioid use measured at the 6 month endpoint for the R33 and 12month endpoint for the R01. Self-reported substance use is the recommended approach for intervention studies.[97] Days of illicit opioid use is defined as the number of days in which opioids other than MAT (buprenorphine or methadone) are used. Time-Line Follow-Back Interview (TLFB)[3, 4] will be used to assess opioid use, other illicit drugs, marijuana, and alcohol use. Participants will be asked first to identify what substances were used in the previous 90 days at each time assessment point (scheduled every 90 days). The participant will then be asked to use a calendar to retrospectively estimate their substance use, for each of the identified substances. Days of other illicit substance use is defined as the number of days (e.g. cocaine, methamphetamine, hallucinogens, or non-prescribed benzodiazepine) are reported using the TLFB.

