1. STUDY OBJECTIVES

1.1 Primary Objective

Primary Objective and Hypotheses

The primary objective is to evaluate the effectiveness of MABT + TAU compared to TAU only in reducing opioid use (OU) and other illicit substances (e.g. methamphetamines, etc.).

Primary hypothesis: MABT+TAU will result in significantly fewer days of OU compared to TAU only from baseline to 12 months.

Secondary hypothesis: MABT+TAU will result in significantly fewer days of non-opioid illicit drugs compared to TAU only from baseline to 12 months.

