3. STUDY DESIGN

Design Overview: A two-group (n = 165/165), randomized, repeated measures design will be employed. Three hundred thirty individuals with OUD engaged in medication treatment will be recruited at one of five outpatient treatment sites: Harborview Medical Center, Country Doctor Community Health Centers, North Olympic Healthcare Network, Cascade Medical Advantage, and Evergreen Treatment Services. Enrolled patients will be individually randomized within sites to receive MABT+TAU (experimental group), or TAU alone (control). Assessments will be administered at baseline, post-intervention (3 months from baseline), and at 6, 9 and 12 months follow-up. An additional six sessions of MABT will be offered to those randomized to MABT who have continued substance use at six months.

Randomization: Following baseline data collection, participants will be randomized to treatment group by the Research Coordinator. [name], the project statistician, provided a randomization program programmed in Microsoft BASIC. Randomization will be specific to each study site and stratified by sex (approximately equal numbers of men and women assigned to each study group at each site) and baseline self-reported chronic pain. The algorithm used for randomization is a modification of a minimization method [96] based on an overall imbalance score which measures how far out of balance (within strata) the study is for a given set of random assignments. Participants will be informed of their assignment within one week of the initial appointment. Prior MABT studies showed no loss due to randomization to treatment group, thus we do not expect randomization to precipitate significant attrition. The Research Coordinator at each facility will not be blind to condition and will inform participants of their treatment condition and MABT therapist.

Measures: The outcome measures are described below (see also Table 1 in Précis).

Primary Objectives: The primary outcome is patient-reported days of illicit opioid use. Self-reported substance use is the recommended approach for intervention studies.[97] Days of illicit opioid use is defined as the number of reported days of use in last 90 days (baseline assessment) or since and including the last assessment date (follow-up assessments) in which opioids other than MAT (buprenorphine or methadone) are reported.

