9.2 Sample Size and Randomization

Sample Size Calculation/Power Analysis:

Primary Objective The power for the primary aim of this study was determined for change in the days percent abstinent from opioids on the Timeline Followback Interview (TLFB) between the study's two arms (MABT +TAU, and TAU only) from baseline to 6 months (R33 aim) and baseline to 12 months (R01 aim). The power analysis was based on the prior MABT SUD R01 study (N=187), in which the proportion of abstinent days for MABT + TAU was 88.6 compared to 80.0 for TAU at 12 month follow-up.[90] Unlike the count data used to assess the number of days abstinent, proportional data is based on exact binomial confidence intervals and thus provides reliable and appropriate data to use for sample size calculation. The magnitude of effect in this prior R01 is expected to be similar for baseline to 6 month (R33) and baseline to 12-month effect for MABT + TAU vs. TAU (R01) in the current study.

A sample of 330, with an expected loss to follow-up of 20%, allows for .80 power to detect a minimum difference in proportion in days abstinent between MABT and TAU of .14, alpha =.05, two-tailed. Loss to follow-up is not expected to vary significantly due to treatment assignment. Since the actual analyses allow GEE models to analyze five time points (0, 3, 6, 9, 12 months) simultaneously for the R01 study, power will very likely be higher than these conservative estimates.

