9.6 Data Analyses

Primary Analysis To test the primary hypotheses, generalized linear regression models for dependent data will be used to compare percent days abstinent from opioid use in the two study groups between baseline to 6 months for the R33 study aims, and baseline to 12 months for the R01 study aims. Sensitivity analyses will also explore modeling opioid use as percent days abstinent during the assessment periods using Generalized Estimating Equations (GEE) [106] with a logit link and an exchangeable correlation structure. We will fit difference within group correlations structures (unstructured, independent, exchangeable, autoregressive) seeking the correlation structure that combines the fewest parameters with the best measure of fit using Akaike information criterion (AIC) and Bayesian information criterion (BIC). The logarithm of the total number of days in the assessment period will be included as an offset variable to account for the time at risk of relapse. The same analysis will be done to examine percent days abstinent on other illicit drugs and alcohol.

Secondary Analyses Analyses of secondary outcomes (mental and physical health outcomes and opioid craving) will utilize GEE as described above. Longitudinal analyses will examine treatment by time interactions on each of the outcomes. Analyses of retention in medication-assisted treatment will be done using a test of proportions retained in MAT as well as the log-rank test to compare survival curves. A sensitivity analysis will use Cox regression to adjust for pre-treatment covariates. Last, we plan to include exploratory analyses to also examine treatment by gender interactions.

Exploratory Analysis Linear regression model using GEE will be used to explore the effect of additional MABT dose on days abstinent from opioid use and related health outcomes at 12 months among the MABT 6 month non-responders compared to control non-responders. Characteristics of responders will be compared to those of non-responders using t-tests, chi-square, or Fisher's exact tests.

In addition, we will explore the relationship with dose, within the MABT group. Dose response functions will be estimated thorough a regression approach treating the number of sessions as the continuous treatment variable. Such models are appropriate when the treatment intensity is endogenous (that is, selection into treatment depends on both observable and unobservable factors).

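### The primary hypothesis is set at 12 months only, but the outcome, power and analysis sections set primary comparisons at both 6 and 12 months, with three wordings of the outcome and no hierarchy, alpha split or success rule

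*Combined protocol and SAP*

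**What the plan says.** **Time point.** Section 1.1 states the primary hypothesis as "MABT+TAU will result in significantly fewer days of OU compared to TAU only from baseline to 12 months", and Section 9.1 repeats it. Three later sections add a 6-month comparison at the same level:

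- Section 9.2 determines power for change "from baseline to 6 months (R33 aim) and baseline to 12 months (R01 aim").
- Section 9.5.1 has the primary outcome "measured at the 6 month endpoint for the R33 and 12month endpoint for the R01".
- Section 9.6, under its primary analysis, will "compare percent days abstinent from opioid use in the two study groups between baseline to 6 months for the R33 study aims" and likewise to 12 months for the R01.

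**Alpha.** A significance level appears once, in Section 9.2: the sample "allows for .80 power to detect a minimum difference in proportion in days abstinent between MABT and TAU of .14, alpha =.05, two-tailed". It is not assigned to either time point. No section gives a testing order, a split of alpha, or a rule on whether one or both time points must succeed.

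**Variable.** Section 3 says: "The primary outcome is patient-reported days of illicit opioid use". Section 9.1 agrees. Section 9.5.1 says: "The primary outcome is patient-reported days of abstinence from illicit opioid use". Sections 9.2 and 9.6 use percent days abstinent, and Section 9.6 then lists percent days abstinent again among its sensitivity analyses.

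**Recall window.** Section 3 counts follow-up days from the last assessment. Section 9.5.1 asks about the previous 90 days. Sections 6.2.4 and 6.2.5 allow each follow-up visit to fall 2 weeks early to 4 weeks late.

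**The concern.** A reader of Sections 1.1 and 9.1 would expect one primary test. A reader of Sections 9.2, 9.5.1 and 9.6 would expect two, and could not tell which decides the trial. If either may be presented as the primary result, there are two chances of a false positive and the stated .05 covers only one of them.

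The two results could well differ. Under Section 5.1, MABT participants with continued use at 6 months are offered six more sessions before the 9-month assessment. Month 6 therefore compares the initial course with TAU, and month 12 compares the stepped-care strategy with TAU. If they disagree, no rule says what the trial concluded.

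The unsettled variable adds a further choice. With a recall window of varying length, counts of days and percentages of days can rank the same participants differently.

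**Working it through.** **1. The plan's own power figure.** Section 9.2 gives .80 power for a difference of .14: "A sample of 330, with an expected loss to follow-up of 20" per cent. Evaluable per arm = 330 × .80 / 2 = 132. The section does not say which rate anchors the .14. Assume .886 (the prior study's MABT rate, Section 9.2) against .886 − .14 = .746, with a continuity-corrected two-proportion test:

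- corrected difference = .14 − 1/132 = .1324
- null SE = √(2 × .816 × .184 / 132) = .0477
- alternative SE = √((.886 × .114 + .746 × .254) / 132) = .0469
- power = Φ((.1324 − 1.96 × .0477) / .0469) = Φ(.83) = .797

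The stated .80 is reproduced on that anchor. Without the correction the same rates give .839. Other anchors move it, again uncorrected: .94 against .80 gives .927, and .80 against .66 gives .729. The calculation is used below only to price the remedies.

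**2. Type I error under each reading.** With one test at 12 months, the error is .05. With two two-sided .05 tests and success on either, it is 1 − P(|Z₁| < 1.96 and |Z₂| < 1.96), where Z₁ and Z₂ are bivariate normal with correlation ρ. At ρ = 0 this is 1 − .95² = .0975, and the upper bound for any ρ is .05 + .05 = .10. The documents give no ρ, so a range is shown. The last column counts only false positives that favour MABT, for which a single test has .025.

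| Assumed ρ | Either test rejects | Favouring MABT only |
|---|---|---|
| 0 | .098 | .049 |
| .3 | .095 | .048 |
| .5 | .091 | .045 |
| .7 | .084 | .042 |
| .9 | .070 | .035 |

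**3. Do the outcome wordings matter?** Over one fixed window, days used and days abstinent are exact complements and the percentage only rescales them. They separate when the window varies. For the final assessment under Section 3's definition, with visits at weeks 39 and 52:

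- shortest window: week 43 to week 50 = 7 weeks = 49 days
- longest window: week 37 to week 56 = 19 weeks = 133 days

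Take a participant abstinent on 80% of days throughout. The same behaviour yields 39 to 106 abstinent days (.8 × 49 to .8 × 133) and 10 to 27 days of use (.2 × 49 to .2 × 133). The percentage stays at 80. This shows that the wordings are not interchangeable. It does not give an alpha figure, because no section plans three tests.

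**4. Cost of the remedies.**

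- 12 months as sole primary, with 6 months next in fixed sequence: error .05; 12-month power unchanged.
- Half of alpha (.025) at each time point: error at most .05. Power for .14 falls from .797 to .707 (corrected) or from .839 to .760 (uncorrected). Restoring .80 with the correction needs 159 evaluable per arm, so 318 / .80 = 397.5, about 398 enrolled.

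**The case against.** A reader might infer that the plan tests both time points at .05 each, so that alpha is simply not held. The documents do not go that far. The .05 is stated once and not per time point, and no section says that a win at either time is a trial success. Section 9.1 says there is one primary objective with one primary hypothesis and puts it at 12 months. The 6-month text always carries the R33 label. On that reading the error is .05, and a disagreement is settled by month 12. This part of the objection stands, so the inflation is conditional.

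A reader might also assume that both tests use the same participants. The Précis says the 12-month analyses will have a larger sample, which leaves open a smaller set at 6 months, although Section 9.2 gives one sample of 330 for both aims. The overlap is unsettled, which is another reason to show a range for ρ. Because the 6-month data also feed the longitudinal analysis to 12 months, the values at higher correlation are the more credible ones.

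Nor do the three wordings amount to three chances of success. Power and the primary analysis both use percent days abstinent. The 90-day window in Section 9.5.1 would make the two counts complements. Section 9.6 also plans an offset for the length of the assessment period. Whether that offset suits the model is a separate question.

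What the objection does not remove is the contradiction. Section 1.1 cannot be relied on while Sections 9.2, 9.5.1 and 9.6 say otherwise. The grant labels do not resolve it either, since no section treats R33 and R01 as separate trials with separate error budgets.

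**Conclusion.** The plan contradicts itself on the primary time point and does not settle the primary variable. If either time point can carry the primary claim, two-sided type I error is about .07 to .098 for an assumed correlation of .9 to 0. Counting only results that favour MABT, it is .035 to .049 against .025. If Section 1.1 governs, .05 holds and the other three sections need correcting. The documents do not say which reading applies, so a flat statement that alpha is exceeded is not supported. The mixed outcome wordings and recall windows are a real but separate inconsistency: they leave the analyst a choice and add no calculable error.

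**What to change.** Before any comparison by arm is made:

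- Name percent days abstinent from illicit opioids at 12 months, MABT+TAU against TAU, as the sole primary outcome. This keeps Section 1.1's time point and the variable already used in Sections 9.2 and 9.6.
- Make 6 months a key secondary outcome, claimed as confirmatory at .05 only if the 12-month test is significant. The order in the hierarchy controls the error, so the 6-month analysis need not wait for the 12-month data to be locked, provided it is not reported as confirmatory before then.
- Use the same variable and one recall window in Sections 1.1, 3, 9.1, 9.2, 9.5.1 and 9.6, and remove percent days abstinent from the list of sensitivity analyses.
- State whether the 6-month analysis uses all randomised participants or a subset.

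The cost is wording, plus a 6-month (R33) claim that depends on the 12-month result. Power at 12 months does not change. If the R33 claim must stand alone, splitting alpha is valid, at the loss of power or the larger sample shown in the working.

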9.5.2 Secondary Outcomes

Measures of mental health (distress symptoms and emotional well-being) will include three well-validated scales for diagnostic screening: the 9-item PHQ-9 to screen for depression[6, 7], the 7-item ($\alpha = .92$) GAD-7 for anxiety[8], and the Posttraumatic Stress Disorder Checklist for DSM-5 (PCL-5),[9] which assesses symptoms of post-traumatic stress on a Likert-type scale with 20 items ($\alpha = .94$). The 4th measure, the Difficulty in Emotion Regulation Scale short form (DERS-SF)[10, 99] assesses difficulties in the modulation of emotional arousal. There are 18 items on a Likert-type scale (DERS $\alpha = .93$; DERS short form α ranges from .78 to .91 with original DERS subscales) and four subscales that assess the degree of awareness, understanding, and acceptance of emotions, and the ability to act in desired ways regardless

of the emotional state. The 5th and 6th measures, the Freiberg Mindfulness Questionnaire (FMQ) with 14 items[14], and the Multidimensional Assessment of Interoceptive Awareness (MAIA)[15] with 32 items on a Likert-type scale are used to assess skills learned in the intervention.

Opioid craving will be assessed using a single item numeric scale.[5] Participants are asked: “On a scale of 0-10, please indicate how much craving you have experienced during the past week,” with responses anchored at “0=no craving at all” and “10-strongest craving ever”. Retention will be defined as days retained in the program, or time to program discharge. Program discharges are documented in the electronic medical record (EMR) and date of discharge will be extracted from the record.

Physical symptoms will be assessed using the Medical Symptoms Checklist (MSC) and pain severity and interference using the Brief Pain Inventory (BPI). The MSC measures the frequency (0-8 scale) and severity (0-10 scale) of 29 common physical symptoms.[19] The BPI is a validated, widely used measurement tool for assessing clinical pain. In the U.S. it has been validated in non-cancer patients with pain[18] and HIV-infected patients.[100] The assessment includes 11 questions which provide information on pain severity and pain interference in the past week. Participants are initially asked if they have experienced any significant pain in the past week, and if they respond positively they answer subsequent questions about duration of pain, pain severity and interference. Pain severity is rated from 0 (“no pain”) to 10 (“worst pain imaginable”), and participants are asked to rate their current pain as well as pain at its worst, at its best, and on average in the past week. Pain interference includes information on the impact of pain on general activity, walking, work, mood, enjoyment of life, relations with others, and sleep, asking the participant to rate interference on a scale from 0 (“does not interfere”) to 10 (“completely interferes”), and is reported as the mean of seven questions. Participants who responded that they had no pain in the past week will be coded “0” for pain severity and interference. The BPI will be supplemented with a single question on duration of currently reported pain in order to establish whether the pain is acute or chronic.

Table 1: Outcomes Measurement Schedule

Concept	Measure	Assessment Time-Point (from baseline)				
		Baseline	12 weeks	24 weeks	39 weeks	52 weeks
Baseline and Descriptive Information						
Demographic/Health History	Health History Form[1].(EHR)	X				
Trauma history	TLEQ[2]	X				
Economic Indicators	Employment, Health Utilization, Legal Status	X	X	X	X	X
Substance Use						
Substance use	TLFB Interview[3, 4]			X	X	X
	Urine Toxicology	X	X	X	X	X
	Opioid Craving [5]	X	X	X	X	X
	Treatment Retention (EHR)	X	X	X		X
Mental Health Distress, Emotional Well-being, Physical Health Distress and Pain						

Distress (Depression, Anxiety PTSD Symptoms)	PHQ-9[6, 7]	X	X	X	X	X
	GAD-7[8]	X	X	X	X	X
	PCL-5[9]	X	X	X	X	X
Emotion Regulation Difficulties	DERS-SF[10]	X	X	X	X	X
Mindfulness and Interoceptive Awareness Skills	FMQ [14]	X	X	X	X	X
	MAIA [15]	X	X	X	X	X
Co-morbid Pain and Interference	BPI[18]	X	X	X	X	X
Physical Symptoms	MSC [19]	X	X	X	X	X
Intervention Satisfaction						
Treatment satisfaction and perceived skills*	MABT Follow-up Questionnaire		X		X	

* MABT group only; NA = not applicable; EHR = Electronic Health Records.

9.6 Data Analyses

Primary Analysis To test the primary hypotheses, generalized linear regression models for dependent data will be used to compare percent days abstinent from opioid use in the two study groups between baseline to 6 months for the R33 study aims, and baseline to 12 months for the R01 study aims. Sensitivity analyses will also explore modeling opioid use as percent days abstinent during the assessment periods using Generalized Estimating Equations (GEE) [106] with a logit link and an exchangeable correlation structure. We will fit difference within group correlations structures (unstructured, independent, exchangeable, autoregressive) seeking the correlation structure that combines the fewest parameters with the best measure of fit using Akaike information criterion (AIC) and Bayesian information criterion (BIC). The logarithm of the total number of days in the assessment period will be included as an offset variable to account for the time at risk of relapse. The same analysis will be done to examine percent days abstinent on other illicit drugs and alcohol.

Secondary Analyses Analyses of secondary outcomes (mental and physical health outcomes and opioid craving) will utilize GEE as described above. Longitudinal analyses will examine treatment by time interactions on each of the outcomes. Analyses of retention in medication-assisted treatment will be done using a test of proportions retained in MAT as well as the log-rank test to compare survival curves. A sensitivity analysis will use Cox regression to adjust for pre-treatment covariates. Last, we plan to include exploratory analyses to also examine treatment by gender interactions.

Exploratory Analysis Linear regression model using GEE will be used to explore the effect of additional MABT dose on days abstinent from opioid use and related health outcomes at 12 months among the MABT 6 month non-responders compared to control non-responders. Characteristics of responders will be compared to those of non-responders using t-tests, chi-square, or Fisher's exact tests.

In addition, we will explore the relationship with dose, within the MABT group. Dose response functions will be estimated thorough a regression approach treating the number of sessions as the continuous treatment variable. Such models are appropriate when the treatment intensity is endogenous (that is, selection into treatment depends on both observable and unobservable factors).

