6.2.3 Blinding

The statistician will be blind to study group. The RC at each facility will not be blind to condition and will inform participants of their study group condition.

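### Section 9.6 reads most naturally as an unadjusted change-from-baseline test; adjusting for the baseline value would be more precise, and the parameter to be tested should be named

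*Combined protocol and SAP*

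**What the plan says.** Section 9.6 gives the primary model only as a class: "generalized linear regression models for dependent data will be used to compare percent days abstinent from opioid use in the two study groups". It adds a logit-link GEE as a sensitivity analysis, an offset for the log of days in the period, and a search over working correlations: "We will fit difference within group correlations structures (unstructured, independent, exchangeable, autoregressive"). For the secondary outcomes it refers back to the same GEE and adds: "Longitudinal analyses will examine treatment by time interactions on each of the outcomes".

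Section 9.2 says "The power for the primary aim of this study was determined for change in the days percent abstinent from opioids", takes as its input that "the proportion of abstinent days for MABT + TAU was 88.6 compared to 80.0 for TAU at 12 month follow-up", and expects extra power because the analysis allows "GEE models to analyze five time points (0, 3, 6, 9, 12 months) simultaneously". Section 9.5.1 sets the endpoint at 6 months for the R33 and 12 months for the R01.

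Allocation is minimised on site, sex and self-reported chronic pain (sections 3, 4.3, 6.2.2 and 9.2). The only covariate adjustment in the plan concerns retention: "A sensitivity analysis will use Cox regression to adjust for pre-treatment covariates". Retention also has its own named tests (proportions and log-rank), so this point does not extend to it.

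**The concern.** Section 9.2 makes month 0 one of the responses, and 9.6 speaks of a comparison from baseline and of arm-by-time terms. Nothing says whether the two arms share a baseline mean, whether the baseline value is instead a covariate, or which coefficient carries the primary test. If the baseline means are free, the arm-by-12-month term is a difference in change scores. That spends information, because the noise in the baseline measurement is carried into the comparison in full.

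At stake is precision in the primary comparison. A second matter is that the tested parameter would be settled after the protocol. Section 6.2.3 limits that: "The statistician will be blind to study group". It does not remove it, since 9.6 also asks for analyses by number of MABT sessions, which exist in one arm only.

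**Working it through.** **1. The plan's own figure.** 330 × 0.80 = 264, or 132 per arm (section 9.2). The stated result is 0.80 power for a difference of 0.14, two-sided alpha 0.05. Section 9.2 does not say which rate the 0.14 is measured from. Comparing two independent proportions with pooled variance:
- 0.886 against 0.746 with continuity correction needs 133 per arm, against 132 available; without the correction, 132 per arm gives power 0.839.
- 0.72 against 0.86 without correction gives 0.801.

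So the figure reproduces under an assumed anchor rate. This calculation has no baseline, time or covariate term, so it does not show which contrast was intended.

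**2. Variance of the candidate contrasts.** Assume a linear model, equal variance at baseline and 12 months, and correlation rho between them. The documents do not give rho, so 0.3, 0.5 and 0.7 are used. Relative to the unadjusted 12-month difference (variance 1):
- change from baseline, free baseline means: 2(1 − rho) = 1.40, 1.00, 0.60
- baseline as covariate: 1 − rho² = 0.91, 0.75, 0.51
- ratio: 2(1 − rho)/(1 − rho²) = 2/(1 + rho) = 1.54, 1.33, 1.18

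At rho below 0.5 the change contrast is less precise even than ignoring baseline.

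**3. What that means for power.** For 0.80 power the noncentrality is 1.960 + 0.842 = 2.802. Section 9.2 words the power for change but feeds in 12-month proportions, so both anchors are shown.
- If 0.80 belongs to the change contrast, adjustment gives Phi(2.802 × sqrt(2/(1+rho)) − 1.96) = 0.94, 0.90, 0.86.
- If 0.80 belongs to the unadjusted 12-month contrast, the table applies. The last three rows also assume compound symmetry.

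| Contrast | rho 0.3 | rho 0.5 | rho 0.7 |
|---|---|---|---|
| Change, free baseline means: Phi(2.802/sqrt(2(1−rho)) − 1.96) | 0.66 | 0.80 | 0.95 |
| Baseline-adjusted: Phi(2.802/sqrt(1−rho²) − 1.96) | 0.84 | 0.90 | 0.98 |
| Joint 4-df arm-by-time, constant effect | 0.66 | 0.82 | 0.97 |
| Joint 4-df arm-by-time, linearly growing effect | 0.54 | 0.71 | 0.92 |
| Unadjusted average of follow-ups, constant effect | 0.98 | 0.94 | 0.89 |

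These are relative illustrations, not estimates of this trial's power. The last three rows show why the test parameter needs naming.

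**4. Logit link.** A simulation (N = 264, five 90-day periods, 12-month means 0.80 and 0.886, assumed between-person spread, observed rho 0.30, 0.50, 0.72) gave effective variance ratios of 1.41, 1.23 and 1.06. The linear formula predicts 1.54, 1.33 and 1.17 there. Only the ratios are used, because the absolute power depends on the assumed spread.

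**5. Constrained baseline means.** This route recovers the precision only if the working correlation lets baseline inform the 12-month estimate, which independence does not. Independence is on the candidate list but unlikely to be chosen. Under a Gaussian working likelihood with 264 people, five times and rho 0.3, exchangeable is better by 264 × −ln[(1−0.3)⁴(1+4×0.3)] − 2 = 264 × 0.638 − 2, about 166 AIC units.

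**6. Allocation factors.** In the same simulation, adding site, sex and pain to the baseline-adjusted model raised power by at most 0.016, with the factors assumed to explain up to 10% of variance. If follow-up values alone were modelled without them, the type I error would be 2(1 − Phi(1.96/sqrt(1−R²))) = 0.048, 0.044, 0.039 at assumed R² of 0.02, 0.05, 0.10. That is slightly conservative.

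**7. Secondary scales.** Section 9.2 claims 80% power at 0.4 SD. With 132 per arm, an unadjusted 12-month contrast has z = 0.4/sqrt(2/132) = 3.25 and power 0.90. A change contrast has 0.78, 0.90, 0.99 at rho 0.3, 0.5, 0.7.

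**The case against.** The best reply is that much of the model is stated. Section 9.5.1 fixes the endpoint times, 9.2 speaks of change, and 9.6 names arm-by-time terms, so a reader would arrive at the arm-by-12-month term without help. That stands in part: it is wrong to infer that the plan has no primary contrast. What remains open is whether the test is that single term or a joint one, and how baseline enters. If the natural reading is right, the plan has landed on the less precise option.

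The logit results concern a sensitivity analysis, since 9.6 does not state the primary link. They serve only to show that the linear gain is an upper guide. A reader might also infer that the trial is underpowered. The documents do not support that: every power figure above is anchored at an assumed 0.80, and the secondary-outcome claim roughly survives even at rho 0.3.

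Nor should one say that the allocation factors are irrelevant to a change contrast. That holds only if their effects are the same at baseline and at 12 months. Section 4.1 admits buprenorphine patients after four weeks and methadone patients after 90 days, while the baseline interview looks back 90 days. Site may therefore predict change.

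**Conclusion.** The point holds as a matter of precision, at the level of something to consider. Read as written, the primary and GEE-based secondary analyses are most naturally unadjusted change contrasts. In a linear model these have 1.54, 1.33 or 1.18 times the variance of a baseline-adjusted contrast at assumed rho 0.3, 0.5 or 0.7. The gain from adjusting is smaller under a logit link and close to nil at high rho.

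Two stronger readings are not supported. A reader might infer bias or excess false positives from the missing adjustment, but randomisation makes the change contrast unbiased, and leaving out the allocation factors errs, if anything, towards conservatism. A reader might also infer that an independence working correlation will be used; it is only a candidate, and selection on fit would almost certainly reject it. The size of the benefit rests wholly on a correlation that the documents do not give.

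**What to change.** In section 9.6, for the GLM and GEE outcomes:
- Model the 3, 6, 9 and 12 month values with the baseline value of the same outcome as a covariate. Alternatively, keep baseline as a response with the arm means constrained equal and rule out an independence working correlation.
- Name the arm difference at 12 months (6 months for the R33 aim) as the primary test, with robust standard errors.
- Include site, sex and baseline chronic pain as fixed effects because allocation was minimised on them; expect little gain.
- Where a logit link is used, report the standardised difference in percent days abstinent, since a covariate-adjusted logit coefficient is no longer the marginal effect.
- Keep the unadjusted model as a sensitivity analysis.

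The cost is a few sentences and a standardisation step. No new data are needed: section 6.2.2 places the baseline interview and survey before randomisation.
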